7.5. Dose Titration Criteria

Dose titration may follow the scheduled dosing regimens described in Section 7.3 or occur due to tolerability concerns.

Dose titrations may involve increases or decreases in dosing frequency and are dependent on tolerability (as assessed by a review of AEs and safety laboratory results). In general, down-titration may be done in response to tolerability concerns and can occur at any time.

Up-titration will be done per protocol based on tolerability, as assessed by the Investigator based on response, or following resolution of a tolerability concern that previously led to down-titration. Up-titrations may only occur to the maximum dose and frequency indicated as defined in [Section 7.3](#).

Scheduled Dose Titration - After initiation of OCA or matching placebo, titration may be considered as early as the Week 12 Visit. Subsequent titrations in dose for patients may occur no earlier than 6 weeks following an up-titration.

Tolerability Dose Titration - Investigators may decrease the dosing frequency or dose as considered clinically appropriate (eg, tolerability).

7.5.1. Pre-Titration Tolerability Assessment Requirements

Tolerability of investigational product must be assessed prior to titrating a patient to a higher dose. To determine if a patient is eligible for a dose titration refer to [Section 7.3](#).

7.6. Close Observation

If investigational product is interrupted or discontinued as described in [Section 8.4](#), patients should be closely monitored (contacted by the site a minimum of every 2 weeks and scheduled visits every 6 weeks; if returning to the site for a scheduled visit is not feasible, use of a local lab may be permissible at the Investigator's discretion). At a minimum, the following assessments should be conducted at each study visit:

- Physical exam and thorough review of patient reported signs and symptoms,
- Liver biochemistry (including ALP, ALT, AST, GGT, total and conjugated bilirubin, creatinine, and albumin), prothrombin time (PT)/INR, serum electrolytes, and assessment of Child Pugh (only if the patient is at the study site) and MELD scores.

In addition, a trough pharmacokinetic sample for assessment of OCA serum drug levels and its major metabolites should be obtained in any patient who develops an AE that is indicative of or consistent with hepatic injury or decompensation.

The following additional monitoring procedures should be performed for events of potential hepatic injury (per FDA Guidance for Industry on Drug Induced Liver Injury) or suspected hepatic decompensation based on criteria described in [Section 7.4.1](#), [Section 7.4.2](#), and [Section 7.4.3](#). These cases need to be discussed with the Sponsor's Medical Monitor:

- Repeating liver biochemistry and function tests as described in [Section 7.4.2](#). Frequency of retesting can decrease to once a week or less if abnormalities stabilize or the study drug has been discontinued and the patient is asymptomatic, as clinically indicated.
- Obtaining a more detailed history of symptoms and prior or concurrent diseases.
- Obtaining a history of concomitant drug use (including nonprescription medications and herbal and dietary supplement preparations), alcohol use, recreational drug use, and special diets is important. Concomitant drugs with potential hepatotoxicity should be recorded and discontinued unless alternative therapies are not available. In the case of concomitant drugs potentially hepatotoxic, continued use of investigational

- product should be discussed with the Sponsor's Medical Monitor. The patient may be discontinued from investigational product, if clinically appropriate.
- Obtaining a history of exposure to environmental chemical agents or herbal supplements which may be associated with liver toxicity.
 - Ruling out acute viral hepatitis types A, B, C, D (in those thought to have acute HBV infection), and E; autoimmune or alcoholic hepatitis; Wilson's disease, hypoxic/ischemic hepatopathy; and biliary tract disease.
 - Investigators should consider testing for Hepatitis E virus when assessing for hepatic decompensation as infection with Hepatitis E virus in patients with chronic liver diseases such as PBC may rapidly worsen with signs and symptoms similar to drug induce liver injury (Kumar 2013)
 - Obtaining additional tests to evaluate liver function, as appropriate (e.g., INR, direct bilirubin).
 - Seeking hepatology consultation, if the Investigator is not a hepatologist

7.7. Criteria for Study Termination

The Sponsor (Intercept Pharmaceuticals, Inc.) reserves the right to terminate the study at any time. It is normal procedure to review the emerging clinical and safety data. As a result of such a review or a recommendation by the Data Monitoring Committee (DMC), it may be necessary to stop the study before all patients have completed the study. In addition, the Sponsor may terminate the study at an investigational site at any time (eg, Good Clinical Practice [GCP] noncompliance or poorly performing sites, as determined by the number of patients enrolled or the quality of the study data).

The Investigator and/or Sponsor (or designee) must notify the Institutional Review Board/Independent Ethics Committee (IRB/IEC) of discontinuation of a site or the study and the reason for doing so.

Investigators will be informed by the Sponsor as to when the final study visit is to be completed, and should then schedule all patients for the end of study (EOS) or end of treatment (EOT) Visit.

8. SELECTION AND WITHDRAWAL OF PATIENTS

8.1. Patient Population

This study will be conducted at approximately 35 international study sites with experience in treating patients with PBC with moderate to severe hepatic impairment defined as CP-B and CP-C. Prospective patients will be identified primarily from the hospital and/or physician's database of patients with PBC, or may be referred from other physicians. Patients may self-refer to an Investigator if they become aware of the study through local, national, or international PBC patient societies, forums, or networks.

8.2. Patient Inclusion Criteria

1. A definite or probable diagnosis of PBC (consistent with American Association for the Study of Liver Diseases [AASLD] and European Association for the Study of the Liver [EASL] Practice Guidelines [Lindor 2009, EASL 2009]), defined as having ≥ 2 of the following 3 diagnostic factors:
 - History of elevated ALP levels for at least 6 months
 - Positive antimitochondrial antibody (AMA) titer or if AMA negative or low titer ($\leq 1:80$), PBC-specific antibodies (anti-GP210 and/or anti-SP100) and/or antibodies against the major M2 components (PDC-E2, 2-oxo-glutaric acid dehydrogenase complex)
 - Liver biopsy consistent with PBC (collected at any time prior to Screening)
2. Evidence of cirrhosis including at least one of the following:
 - Biopsy results consistent with PBC Stage 4
 - Liver stiffness as assessed by TE Value ≥ 16.9 kPa
 - Clinical evidence in the absence of acute liver failure consistent with cirrhosis including: gastroesophageal varices, ascites, radiological evidence of cirrhosis (nodular liver or enlargement of portal vein and splenomegaly)
 - Combined low platelet count ($< 140\,000/\text{mm}^3$) with:
 - persistent decrease in serum albumin, or
 - elevation in prothrombin time /INR (not due to antithrombotic agent use), or
 - elevated bilirubin ($2 \times \text{ULN}$)
3. Satisfy the criteria of the modified CP classification for hepatic impairment during Screening:
 - Moderate: CP-B (Scores 7 to 9) or
 - Severe: CP-C (Scores 10 to 12)
4. MELD score of 6 to 24 at Screening
5. Age ≥ 18 years
6. Taking UDCA for at least 12 months (stable dose for ≥ 3 months) prior to Day 1, or unable to tolerate or unresponsive to UDCA (no UDCA for ≥ 3 months)
7. Contraception: Female patients must be postmenopausal, surgically sterile, or if premenopausal (and not surgically sterile), be prepared to use ≥ 1 effective method of contraception during the study and for 30 days after the end of treatment visit. Effective methods of contraception are considered to be those listed below:
 - Barrier method, ie, (a) condom (male or female) with spermicide **or** (b) diaphragm with spermicide; or

- Intrauterine device; or
 - Vasectomy (partner); or
 - Hormonal (eg, contraceptive pill, patch, intramuscular implant or injection); or
 - Abstinence, if in line with the preferred and usual lifestyle of the patient (where abstinence is defined as refraining from heterosexual intercourse)
8. Must provide written informed consent and agree to comply with the study protocol.

8.3. Patient Exclusion Criteria

1. Non-cirrhotic or cirrhotic CP-A (Mild; Score 5 to 6)
2. History of liver transplant or organ transplant
3. History of alcohol or drug abuse within 12 months prior to Screening
4. Current hepatic encephalopathy (as defined by a West Haven score of ≥ 2 [[AASLD](#), [EASL 2014](#)])
5. History or presence of other concomitant liver diseases including:
 - a. Hepatitis C virus infection and RNA positive
 - b. Active hepatitis B infection; however, patients who have seroconverted (hepatitis B surface antigen and hepatitis B e antigen negative) may be included in this study after consultation with the Medical Monitor
 - c. Primary sclerosing cholangitis
 - d. Alcoholic liver disease
 - e. Definite autoimmune liver disease or overlap hepatitis
 - f. Gilbert's Syndrome
6. In the opinion of the Investigator, fluctuating or rapidly deteriorating hepatic function prior to randomization
7. Patients with history or presence of hepatorenal or hepatopulmonary syndrome
8. Patients with significant active infection (ie spontaneous bacterial peritonitis)
9. Patients with known or suspected hepatocellular carcinoma
10. History of known or suspected clinically significant hypersensitivity to OCA or any of its components
11. Participation in another investigational product, biologic, or medical device study within 30 days prior to Screening. Participation in a previous study of OCA is allowed with 3 months washout prior to enrollment in this study
12. Mental instability or incompetence, such that the validity of informed consent or ability to be compliant with the study is uncertain
13. UDCA naïve (unless contraindicated)

8.4. Dose Adjustment, Interruption, and Withdrawal from Investigational Product or Study

Investigational product may be temporarily decreased (eg, from 10 mg twice weekly to 5 mg twice weekly, or from 5 mg twice weekly to 5 mg once weekly) or temporarily or permanently stopped based on tolerability concerns. Investigational product may be resumed at the maintenance dose upon resolution of gastroenteritis or worsening renal function or dehydration if there is no evidence of liver injury. For rechallenge following all other dose interruptions (see Table 5), investigational product should be initiated at a lower dose and patients monitored more frequently with up-titration considered based on tolerability.

Adjustments, interruptions, discontinuation, and any rechallenge of investigational product should be implemented per the criteria outlined in Table 5. Patients that discontinue investigational product are expected to continue in the study (and follow the regular visit schedule, with the exception of PK sampling [trough PK may be required in the event of an AE consistent with hepatic injury or decompensation]) until the end of the study, but may withdraw consent at any time.

Table 5: Criteria for Dose Adjustment, Interruption, Discontinuation, and Rechallenge

DOSE ADJUSTMENT		
Criteria	Action Taken with IP	Adjustment
New Onset Severe Pruritus	Drug holiday or less frequent dosing	Return to original dose regimen if tolerated
DOSE INTERRUPTION		
Criteria	Action Taken with IP^a	Rechallenge^b
If liver biochemistries indicative of suspected hepatic injury are identified as exceeding upper threshold criteria and require immediate interruption (see Part A of Table 3) ^c	Interrupt immediately upon initial observation	Patient may be rechallenged after a minimum of 30 days if fully resolved OR stable and approved by the Medical Monitor and Investigator.
Other liver biochemistries indicative of suspected hepatic injury are outside upper threshold criteria upon repeat testing as defined in Part A of Table 3 ^d	Interrupt after confirmation by repeat testing	
Liver biochemistries indicative of potential hepatic decompensation in the absence of symptoms (see Part B of Table 3) ^e	Closely monitor until normalization or stabilization. If values continue to increase relative to the baseline value, interrupt	
Clinical events indicative of hepatic decompensation (see Part B of Table 4)	Closely monitor until normalization or stabilization	The patient may be rechallenged after a minimum of 30 days if fully resolved OR stable and approved by the Medical Monitor and Investigator. IP should be re-initiated at a lower dose (or lower dose frequency) and titrated per Investigator discretion.

Gastroenteritis (established severe abdominal pain, vomiting, diarrhea for more than 4 days)	Interrupt	If no evidence of liver injury is detected, IP may be restarted at the same dose after resolution of intercurrent illness.
Evidence of worsening of renal function or dehydration	Interrupt	
DOSE DISCONTINUATION		
Criteria	Action Taken with IP	Rechallenge
If INR increases ≥ 2.0 in absence of clinical symptoms criteria (unless due to vitamin K deficiency) ^f	Discontinue / No Rechallenge	Discontinue IP permanently and continue to return for scheduled study visits for safety follow-up. Continue to return for scheduled study visits for safety follow-up. Monitor closely for clinical outcomes according to protocol assessments.
If total bilirubin thresholds (Part B of Table 3) are observed in the presence of clinical symptoms of cholestatic hepatitis or hepatic encephalopathy ^f		
Multi-Organ failure requiring hospitalization		
Liver transplantation		
Pregnancy		

Fully resolved = Return to baseline levels or return to within normal limits (WNL). IP = investigational product

^a If patient is unable to be evaluated promptly, study drug must be immediately interrupted.

^b Requires complete documentation of complete resolution or normal/baseline results based on laboratory parameters and symptoms.

^c Total bilirubin baseline \leq ULN and $\geq 3x$ baseline, baseline $>$ ULN and $\geq 2x$ baseline, ALT or AST $> 3x$ baseline (and $>$ ULN)

^d ALT or AST $\geq 2x$ baseline or electrolytes (sodium < 130 mEq/L).

^e Total bilirubin baseline \leq ULN and 1.5 mg/dL increase from baseline OR baseline $>$ ULN and 1.0 mg/dL increase from baseline; INR > 0.3 increase from baseline

^f If INR increases ≥ 2.0 in the absence of clinical symptoms or if or total bilirubin thresholds OR an INR increase from baseline of ≥ 1.5 are observed in the presence of clinical symptoms of cholestatic hepatitis or hepatic encephalopathy.

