Total Bilirubin	Closely monitor until normalization or stabilization.	The patient may be rechallenged after a minimum of 30 days if fully resolved OR stable and approved by the Medical Monitor and Investigator.
Baseline \leq ULN and 1.5 mg/dL increase from baseline	If values continue to increase relative to the baseline value, interrupt IP.	If laboratory values do not normalize, IP should not be restarted.
Baseline $>$ ULN and 1.0 mg/dL increase from baseline		
INR^b	Closely monitor until normalization or stabilization.	The patient may be rechallenged after a minimum of 30 days if fully resolved OR stable and approved by the Medical Monitor and Investigator.
$>$ 0.3 increase from baseline	If values continue to increase relative to the baseline value, interrupt IP.	If laboratory values do not normalize, IP should not be restarted.
\geq 2.0 unless due to vitamin K deficiency	Discontinue IP permanently	Continue to return for scheduled study visits for safety follow up. Monitor closely for clinical outcomes per protocol.
C. Laboratory Criteria for Monitoring Potential Hepatic Decompensation in the Presence of Clinical Symptoms		
Total bilirubin thresholds defined in Part B OR an INR increase from baseline of \geq 1.5 are observed in the presence of clinical symptoms of cholestatic hepatitis or hepatic encephalopathy ^c	Discontinue IP permanently	Continue to return for scheduled study visits for safety follow up. Monitor closely for clinical outcomes per protocol.

IP = investigational product

^a Sodium will be measured as an assessment of liver failure (hyponatremia).

^b Does not apply in patients on anti-coagulants.

^c Symptoms of cholestatic hepatitis includes dark urine and jaundice. Symptoms of hepatic encephalopathy may include lack of awareness, shortened attention span, lethargy, gross disorientation, or coma (unresponsive to verbal or noxious stimuli).

It should be noted that it is difficult to recognize every potential marker of hepatic or renal deterioration. There is no substitute for good medical judgment. Investigators will be reminded to be cautious and mindful in their evaluation of patients' symptoms, signs, and laboratory results. However, for example, a single abnormal laboratory analyte result may be artefactual; accordingly, Investigators will be allowed to implement an alternate follow-up procedure if considered appropriate based on their medical judgement, but only after documented agreement with the Sponsor's Medical Monitor.

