7.4.3. Clinical Criteria for Monitoring for Potential Hepatic Decompensation

Patients will be monitored for potential hepatic decompensation events throughout the study. Clinical criteria for monitoring these events and the interruption/discontinuation of investigational product is summarized in [Table 4](#).

Investigational product should be discontinued permanently if the patient received a liver transplant or experiences multi-organ failure as defined in Table 4, Part A. Patients should continue to return for scheduled study visits for safety follow-up.

Patients who experience other potential hepatic decompensation events defined in Table 4, Part B should be closely monitored until normalization or stabilization. Patients may be rechallenged after a minimum of 30 days if fully resolved OR stable and approved by the Medical Monitor and Investigator.

Table 4: Clinical Criteria for Monitoring Potential Hepatic Decompensation Events and Interruption / Discontinuation of Investigational Product

A. Hepatic Decompensation Events Requiring Mandatory Discontinuation of Investigational Product	
Decompensation Event	Action Taken / Rechallenging Criteria
Liver Transplant Multi-organ failure requiring hospitalization	Discontinue IP permanently and follow patients until normalization/stabilization. Continue to return for scheduled study visits for safety follow up.
B. Hepatic Decompensation Events Requiring Interruption of Investigational Product	

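### The hepatic stopping and restart rules in Tables 3, 4 and 5 conflict on the INR scale, on whether decompensation interrupts drug, and on when drug may be restarted

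*Protocol*

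**What the plan says.** **INR.** Table 3 Part B (Section 7.4.2), which covers laboratory changes without clinical symptoms, has two INR rows. One is a rise of more than 0.3 from baseline. The other is an INR at or above "2.0 unless due to vitamin K deficiency", with permanent discontinuation. Table 4 footnote a repeats the second as a level, with no rechallenge. The discontinuation block of Table 5 (Section 8.4) uses the verb *increases* before the threshold, followed by "2.0 in absence of clinical symptoms criteria (unless due to vitamin K deficiency"), and footnote f repeats that verb. For symptomatic patients, Table 3 Part C reads "Total bilirubin thresholds defined in Part B OR an INR increase from baseline of" 1.5 or more. The matching Table 5 row names only the bilirubin thresholds, and the INR limb appears only in footnote f.

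**Decompensation events.** Table 4 Part B is titled "Hepatic Decompensation Events Requiring Interruption of Investigational Product". Section 7.4.3 says: "Patients who experience other potential hepatic decompensation events defined in Table 4, Part B should be closely monitored until normalization or stabilization". The action cell of Table 4 Part B and the action cell of the corresponding Table 5 row carry the same monitoring instruction. Both then give rechallenge terms.

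**Restart.** Table 3 Part B says: "The patient may be rechallenged after a minimum of 30 days if fully resolved OR stable and approved by the Medical Monitor and Investigator". It then says: "If laboratory values do not normalize, IP should not be restarted". The Table 5 rechallenge cell has the same resolved-or-stable condition, but footnote b on that column reads: "Requires complete documentation of complete resolution or normal/baseline results based on laboratory parameters and symptoms".

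**Precedence.** Section 8.4 tells sites to implement adjustments, interruptions, discontinuations and rechallenge by Table 5. Section 7.4 says drug may be interrupted or discontinued by the criteria of Sections 7.4.2 and 7.4.3, which hold Tables 3 and 4.

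**The concern.** These are the central hepatic safety rules of a trial in patients with moderate to severe hepatic impairment. A site that follows the text literally can reach a different stop or restart decision depending on which table, or which part of one table, it reads.

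This matters for the analysis as well as for conduct. Safety and tolerability is a primary objective, and Table 7 lists discontinuations among its assessments. Exposure, interruptions and the availability of an evaluable PK profile all follow from the same decisions. If the rules are applied unevenly, differences in these outcomes partly reflect how the protocol was read.

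**Working it through.** The plan states no figure to reproduce. The check sets the passages side by side, with simple arithmetic for INR.

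**1. INR scale.** Inputs: the threshold of 2.0 (Tables 3, 4 and 5) and a baseline INR *b*. The protocol gives no expected baseline INR, so *b* is assumed. The range runs from 1.0 to 1.7, the upper value being where the Child-Pugh table (Table 12) starts to score two points.

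- Level reading: stop at INR = 2.0.
- Rise reading: stop at INR = *b* + 2.0.
- Difference: (*b* + 2.0) − 2.0 = *b*.

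| Assumed baseline INR | Level reading | Rise reading | Difference |
|---|---|---|---|
| 1.0 | 2.0 | 3.0 | 1.0 |
| 1.3 | 2.0 | 3.3 | 1.3 |
| 1.7 | 2.0 | 3.7 | 1.7 |

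A patient with a baseline of 1.3 and no symptoms who reaches 2.5 is permanently discontinued under Table 3 Part B. The rise is 2.5 − 1.3 = 1.2, so the Table 5 trigger read as a rise is not met.

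**2. Interrupt or monitor.** The Table 5 row for clinical decompensation events sits in the dose interruption block, whose rows are not uniform:

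- Immediate laboratory triggers, confirmed laboratory triggers, gastroenteritis, and worsening renal function or dehydration: the action cell says to interrupt.
- Asymptomatic laboratory changes (Table 3 Part B): monitor first, and interrupt if values keep rising.
- Clinical decompensation events: monitor, with no instruction to interrupt.

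The block heading alone therefore does not fix the action, because one row in it makes monitoring the first step. The Table 4 Part B title requires interruption, and rechallenge terms only make sense if drug was stopped. Interruption is implied by the headings and the restart terms, but no action cell orders it.

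**3. Restart.** The Table 5 notes define full resolution as return to baseline or to normal limits. Footnote b asks for complete resolution or normal/baseline results, which is essentially that definition. It therefore leaves the *stable* alternative in the same column with no effect. Within Table 3 Part B, a patient whose bilirubin rose, led to interruption and then held steady above baseline for 30 days may be rechallenged with approval under the first sentence. The second sentence bars restart. Taking normalization to include return to baseline does not help, since this patient has not returned to baseline.

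**4. Precedence.** Sections 7.4 and 8.4 point to different tables, and Table 5 refers back to Tables 3 and 4 for its triggers. Ranking the tables would not be enough in any case, because some conflicts lie inside one table: the Table 4 Part B title against its cell, the two sentences in Table 3 Part B, and the Table 5 cell against footnote b.

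**5. Scale of consequence.** Section 15.2 plans about 50 patients randomized 1:1, so 50 / 2 = 25 per arm. One patient classified differently moves an arm's discontinuation or interruption rate by 1/25 = 4 percentage points.

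**The case against.** The best defence is that much of this is loose drafting with a discoverable intent. Table 5 does not say *increases by*. Footnote f attaches the phrase about baseline only to the 1.5 trigger, and two other places state a level, so *increases to* is a plausible reading. Interruption for decompensation is strongly implied. Table 4 footnotes b and c make interruption discretionary only for non-bleeding varices and new-onset ascites, which suggests that it is expected for the listed events. Restart needs Medical Monitor approval, which limits variation between sites.

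This narrows the point but does not remove it. The text does not settle the INR scale, the action cells omit the action, and the Medical Monitor works from the same conflicting restart conditions. The clause in Section 7.4.2 allowing alternate follow-up by agreement covers individual exceptions and does not supply a default.

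A reader might infer more than the documents support:

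- *That the symptomatic INR trigger, a rise of 1.5, contradicts the asymptomatic level of 2.0 because it is usually reached later.* That is a comment on the ordering of clinical triggers. Part C also fires on bilirubin alone.
- *That eligible patients may already meet the level rule on Day 1.* This is an observation about eligibility. Supporting it through MELD needs weights that the protocol does not give.
- *That a symptomatic patient moving from, say, 1.3 to 2.2 falls under no INR rule.* Table 4 footnote a stops drug at 2.0 or more and has no condition about symptoms.

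**Conclusion.** Three conflicts stand in the current protocol text:

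- the INR trigger is a level in two places and possibly a rise in Table 5, with the symptomatic Table 5 row also leaving its INR limb to a footnote;
- interruption for Table 4 Part B events is implied but not instructed;
- restart on stability is both allowed and barred.

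For INR, the possible discrepancy equals the baseline INR. The illustrated range of 1.0 to 1.7 is an assumption, and the discrepancy exists only if Table 5 is read as a rise. The effect on observed discontinuation rates cannot be estimated from the protocol; 4 percentage points per affected patient is the unit of change, not a forecast. The documents do not show that Table 5 was meant as a rise, or that drug was meant to continue through decompensation. No view is taken on which rule is clinically right. Because the rules drive primary safety outcomes and no precedence is stated, they need to be reconciled.

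**What to change.** Reconcile Table 3, Table 4 Part B, Section 7.4.3 and Table 5, including its footnotes b and f, in one amendment. Each trigger should carry:

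- one scale, stated as a level or as a change from baseline;
- one explicit action in the action cell;
- one restart condition, worded the same wherever it appears.

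The symptomatic row of Table 5 should state the same INR limb as Table 3 Part C and footnote f, in whatever form is chosen. Sections 7.4 and 8.4 should name the same governing source. The clinical team decides which version applies.

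The cost is a safety amendment to three tables and the related text, plus a memo to sites. Sample size and visit schedule are unaffected.
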